#### **6.2.2.2. Unfavourable status**

1. Participants not classified as having achieved or maintained culture negative status when last seen, or
2. Participants previously classified as having culture negative status who, following the end of treatment, have two positive cultures without an intervening negative culture (however, see [§3.1.2](#) for an exception), or
3. Participants who had a positive culture not followed by at least two negative cultures when last seen, or
4. Participants dying from any cause during treatment, except from violent or accidental cause (e.g. road traffic accident), not including suicide (e.g., suicide will be considered an unfavourable outcome), or
5. Participants definitely or possibly dying from TB related cause during the follow-up phase, or
6. Participants requiring an extension of their treatment beyond that permitted by the protocol a restart or a change of treatment for any reason except reinfection or pregnancy, or
7. Participants lost to follow up or withdrawn from the study before the end of treatment.

#### **6.2.3. PP Population**

##### **6.2.3.1. Unassessable status (additional exclusions from TB-mITT)**

In addition to those already excluded from the mITT (see [§6.2.1.1](#)) and the TB-mITT (see [§6.2.2.1](#)) analyses, the following participants will be excluded from the PP analysis:

1. Participants lost to follow-up or withdrawn for reasons other than treatment failure (e.g. participant consent or relocation) before the end of treatment, unless they have already been classified as having an unfavourable outcome.

2. Participants whose treatment was modified or extended beyond what is permitted in the protocol for reasons other than an unfavourable therapeutic response to treatment (e.g. an adverse drug reaction), unless they have already been classified as having an unfavourable outcome.
3. Participants not meeting the definition of having received an adequate amount of their allocated study regimen (see §3.3), provided this is not due to an unfavourable outcome.
4. Participants who are classified as “major protocol deviations for analysis” (see §3.5), unless they have already been classified as having an unfavourable outcome on the basis of data obtained prior to the protocol deviation

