## 5. Analysis Populations

Analysis populations are:

- The **Intent to treat (ITT)** population, defined as all participants who were enrolled, whether or not they started treatment.
- The **Safety** population, defined as all enrolled participants who received at least one dose of study treatment. Participants will be analysed as to the treatment they actually received regardless of given allocation.
- The **Modified intent to treat (mITT)** population, defined as all participants who were enrolled and started treatment, excluding any late screening failures.
- The **TB-specific modified intent to treat (TB-mITT)** population, defined as the mITT population with additional exclusions (see below).
- The **Per-protocol (PP)** population, defined as the TB-mITT population with additional exclusions (see below).

For ITT, mITT, TB-mITT and PP; participants will be analysed as to the treatment they were randomised to receive.

For short-term culture conversion endpoints, only the mITT population will be examined.

The TB-mITT population is unique to the TB field and is outlined here (with further details provided in [Appendix §13.3](#)). TB-mITT is a key analysis that has been used in the literature of long-term outcome trials of durable cure in TB, although it has generally been referred to simply as the ‘mITT analysis’. This analysis excludes participants based on data collected post-randomisation. A true mITT analysis, as recognised by regulatory authorities, does not exclude any participants due to missing data post-enrollment.

Thus, for the long-term endpoint of durable cure, the TB-mITT analysis will be considered primary for the purposes of publication, to allow comparison with the rest of the literature in the TB field. However, for regulatory purposes, we recognise that regulatory agencies will consider the mITT analysis primary.

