#### **6.2.3.2. Unfavourable status**

Points 1-6 in §6.2.2.2 Unfavourable status in the TB-mITT Population section above

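### Per-protocol analysis: a treatment change for an adverse drug reaction is both excluded (SAP §6.2.3.1, point 2) and unfavourable (§6.2.2.2, point 6, imported unedited by §6.2.3.2)

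*SAP*

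**What the plan says.** - **Exclusion.** §6.2.3.1, point 2, excludes from PP "Participants whose treatment was modified or extended beyond what is permitted in the protocol for reasons other than an unfavourable therapeutic response to treatment". An adverse drug reaction is the named example. A proviso keeps in anyone already classified as unfavourable.
- **Unfavourable.** §6.2.2.2, point 6, written for TB-mITT, makes unfavourable an extension past what the protocol allows, or "a restart or a change of treatment for any reason except reinfection or pregnancy". An adverse drug reaction is not among the exceptions.
- **Import.** §6.2.3.2 defines unfavourable status in PP as "Points 1-6 in §6.2.2.2 Unfavourable status in the TB-mITT Population section above". Point 6 comes across with no edit.
- **Point 7.** This point, "Participants lost to follow up or withdrawn from the study before the end of treatment", is left out for PP. That matches PP exclusion 1, which removes "Participants lost to follow-up or withdrawn for reasons other than treatment failure (e.g. participant consent or relocation) before the end of treatment".
- **Time anchor.** Exclusion 4 limits its proviso to a classification made "on the basis of data obtained prior to the protocol deviation". Exclusion 2 has no such limit.
- **Use of PP.** §2.2 names PP as one of three populations for the 12-month non-inferiority comparison. PP is also used for 24-month status and time to unfavourable status (§2.4, §7.2.2, §7.2.3) and for both sensitivity analyses in §7.2.1.2.

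**The concern.** One event satisfies two rules that give opposite codings. A participant whose regimen is extended beyond protocol, or changed, because of an adverse drug reaction leaves the PP analysis under one rule and is a PP failure under the other. A programmer who follows §6.2.3.2 literally could code the SAP's own example as unfavourable, against the apparent purpose of exclusion 2.

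Such changes need not be equally common in the two arms, because the regimens differ in drugs and in length (§1.1). If they differ, the coding moves the PP difference itself as well as its precision. The trial is open-label (§1), so a coding left open could also be settled after results by arm are known.

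**Working it through.** **1. The texts side by side**

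| Event, for an adverse drug reaction | §6.2.3.1 point 2 | §6.2.2.2 point 6 via §6.2.3.2 |
|---|---|---|
| Extension beyond protocol | excluded | unfavourable |
| Change of treatment | excluded (a change is a modification) | unfavourable |
| Other modification, if 'change' is read narrowly | excluded | not covered |

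The proviso has two readings.
- If the change itself makes the participant already unfavourable, exclusion 2 is largely emptied, including its own example.
- If only an earlier, separate event counts, exclusion 2 works, but point 6 cannot then apply to these participants as §6.2.3.2 says it does.

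The SAP states neither reading and gives no order for the two rules.

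**2. Size**

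The SAP has no figure on this point, so this is an illustration.

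Inputs from the SAP: 16% unfavourable in control and 13% unassessable (§4); 12% margin against the upper two-sided 95% limit (§7.2.1); 150 × 0.87 ≈ 130 per arm; 196 per arm for analysis if the trial is extended (§13.4). As a check on these inputs, Φ(0.12/√(2 × 0.84 × 0.16/130) − 1.96) = 75.1%, close to the 74% power stated in §4.

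Assumed: rates of such changes ae (experimental) and ac (control); the same failure rate f in both arms among everyone else; a control total of 16% when changes count as unfavourable, so f = (0.16 − ac)/(1 − ac); Wald limits.

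- Excluded: difference 0; SE = √(f(1−f)[1/(n(1−ae)) + 1/(n(1−ac))]).
- Unfavourable: pe = ae + (1−ae)f, pc = 0.16; SE = √(pe(1−pe)/n + pc(1−pc)/n).

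Worked case, 6% v 2% at n = 130:
- f = 0.14/0.98 = 0.1429.
- Excluded: SE = √(0.1429 × 0.8571 × [1/122.2 + 1/127.4]) = 0.0443; upper limit 1.96 × 0.0443 = 8.7%.
- Unfavourable: pe = 0.06 + 0.94 × 0.1429 = 0.1943; difference 0.0343; SE 0.0473; upper limit 0.0343 + 1.96 × 0.0473 = 12.7%.

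| n per arm | Changes, exp. v control | Upper limit, excluded | Upper limit, unfavourable | Opposite sides of 12%? |
|---|---|---|---|---|
| 130 | 2% v 2% | 8.6% | 8.9% | no |
| 130 | 4% v 2% | 8.6% | 10.8% | no |
| 130 | 6% v 3% | 8.5% | 11.8% | no |
| 130 | 6% v 2% | 8.7% | 12.7% | yes |
| 130 | 10% v 6% | 7.8% | 12.9% | yes |
| 130 | 2% v 6% | 7.7% | 4.9% | no |
| 196 | 6% v 2% | 7.1% | 11.0% | no |
| 196 | 8% v 2% | 7.1% | 12.8% | yes |

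**3. Tipping point**

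This is the smallest ae at which the unfavourable coding reaches 12%.

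| Control rate | 130 per arm (gap) | 196 per arm (gap) |
|---|---|---|
| 1% | 4.3% (3.3 points) | 6.2% (5.2 points) |
| 2% | 5.3% (3.3 points) | 7.1% (5.1 points) |
| 6% | 9.1% (3.1 points) | 10.9% (4.9 points) |

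The absolute gap is nearly constant across control rates; the ratio is not. The gap does depend on the other inputs. With 5% other failures and control changes at 2%, the tipping points rise to 7.2% and 8.4% (gaps of 5.2 and 6.4 points). At 117 per arm (10% fewer, assumed), with control at 2% and f as before, the tipping point falls to 4.7%.

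**4. Stratified check**

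§7.2.1 plans a Cochran-Mantel-Haenszel analysis. With Mantel-Haenszel weights over four assumed HIV-by-cavitation strata at 130 per arm, the unfavourable coding gives 12.6% for 6% v 2% and 11.7% for 6% v 3%. Both lie on the same side of the margin as the Wald limits.

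**The case against.** The strongest reply is that the structure already answers the question. §5 builds PP by taking further exclusions from TB-mITT, and a participant outside a population has no outcome coded in it. Exclusion 2 is the more specific rule, and dropping point 7 shows that the authors meant exclusions to come first. This stands as evidence of intent. It does not settle the proviso, which asks about unfavourable status before it lets the exclusion apply. It also does not explain why point 6 was imported whole when point 7 was removed.

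Three further objections stand as limits.
- The wording of the two rules is not identical, so exclusion 2 would not be entirely empty even if point 6 prevailed.
- Every change rate above is assumed, and the 16% and 13% are planning inputs, not PP rates.
- §1 says that the protocol has its own PP population. The protocol is not at hand and may state the order.

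A reader might infer that the main non-inferiority conclusion is at risk. The SAP does not support that. Exclusion 2 applies to PP only. For the long-term endpoint §5 says that "the TB-mITT analysis will be considered primary for the purposes of publication" and expects regulators to treat mITT as primary; this conflict reaches neither.

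A reader might also infer that some fixed multiple of the control rate is needed for the verdict to turn. That holds only if the control rate is fixed: 10% v 6% is 1.7-fold and turns it at 130 per arm, while a control rate of 1% needs 4.3-fold at 130 per arm and 6.2-fold at 196.

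**Conclusion.** The concern holds as a drafting conflict of minor severity. As written, §6.2.3 gives two codings to one participant, including the SAP's own example. Exclusion is the likelier intent, but it is not stated.

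The reach is every PP result: unfavourable status at 12 and 24 months, time to unfavourable status, and the PP sensitivity analyses. For the non-inferiority verdict the coding matters only if such changes are clearly more frequent in the experimental arm. With a 16% control total and otherwise equal failure rates, that means about 3 percentage points at 130 per arm or 5 points at 196; the gap is larger if other failures are rarer. Balanced rates, or the tested imbalance towards control (2% v 6%), leave the verdict unchanged. Since the SAP gives no rates, nothing here shows that a reversal is likely. Confidence is high on the overlap in the text and much lower on any practical effect.

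**What to change.** Make two wording edits before database lock, by a new SAP version or by a note to file, a route the SAP has already used. They concern classification for analysis only.

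(a) In §6.2.3.1, point 2, give the proviso a time anchor like that of exclusion 4: only an unfavourable classification based on data from before the treatment modification or extension keeps the participant in PP.

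(b) In §6.2.3.2, keep points 1-6 of §6.2.2.2 but add that point 6 does not apply to participants excluded under §6.2.3.1, point 2.

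Then reconcile both with the protocol's PP definition. A general statement that exclusions come before classification would not be enough by itself, because the proviso itself asks about unfavourable status. A restart or change of treatment for poor therapeutic response stays unfavourable, since exclusion 2 does not cover it.

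The cost is small: no new data, and a slightly smaller PP set. At assumed rates PP loses about 5 of 260 participants at 2% v 2% (260 × 0.02 = 5.2) and about 10 of 260 at 6% v 2% (130 × 0.06 + 130 × 0.02 = 10.4).

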#### **6.2.3.2. Unfavourable status**

Points 1-6 in §6.2.2.2 Unfavourable status in the TB-mITT Population section above

## **7. Efficacy Statistical Analysis**

All efficacy outcomes will be analysed for superiority with the exception of the proportion of participants who have an unfavourable outcome at 12 months and at 24 months. These will be analysed for non-inferiority with a non-inferiority margin of 12%.

All superiority analyses for efficacy, apart from the interim analysis (see §7.3), will be two-sided and considered statistically significant at the 5% level.

All efficacy analyses will be adjusted for the stratification variables (HIV status and cavitation) unless otherwise stated and considered primary. Unadjusted analyses will also be considered for key endpoints.

Additional baseline covariates listed in §7.4 will be considered for a secondary adjusted analysis for key efficacy endpoints.

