## **4. Sample Size**

For the primary endpoint, time-to-negative culture conversion at 8 weeks, 150 participants per arm (DS-TB participants) will provide more than 99% power (5% two-sided significance) to detect a hazard ratio (HR) of at least 2 (for 4BPaMZ vs. HRZE), assuming 50% of control participants are culture negative by 8 weeks. If only 25% of the control arm remain culture positive at 8 weeks, then this sample size will still retain more than 93% power to detect a HR of least 2. Note, non-randomised MDR participants will not be formally compared to any randomised group.

For the key secondary efficacy endpoint of clinical outcome at 12 months from randomisation, 150 participants per arm will provide 74% power at the two-sided 5% significance level based on assumptions using data from the largest most recently completed phase 3 TB treatment trial which used the same control arm [2]. That is, assuming 16% of participants in the control arm are unfavourable and 13% are unassessable at 12 months post randomisation. A non-inferiority margin of 12% is chosen and justified below.

This trial aims to demonstrate that the experimental regimen administered for 4 months to participants with DS-TB is not inferior to the standard 6-month control regimen using a non-inferiority margin of 12%, chosen based on the following rationale. The best estimate for the treatment effect (also known as M1 in guidance documents for non-inferiority trials) of the current standard treatment (HRZE) is derived from modern clinical trials of this treatment compared to historical, natural history trials. Based on the above reference, an estimate of the favourable rate observed with standard HRZE therapy of 84% is used. The WHO estimates that the case fatality rate for untreated smear positive pulmonary tuberculosis is 70%, and this estimate was confirmed in a systematic review in 2011 [3]. Therefore, an estimate of 30% for the favourable rate of placebo may be contrasted with the 84% favourable rate of the standard HRZE therapy. Based on these data, the best available point estimate for M1 (the overall treatment effect of HRZE, expressed as a risk difference) is 54%. A selection of 12% for M2 (the non-inferiority margin) would represent less than 25% of the point estimate of M1, thus assuring that the lower bound of the NI margin preserves more than 75% of the estimated treatment effect of the HRZE regimen.

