##### 6.1.1.1. Unassessable status (late exclusions)

1. Participants enrolled and later found to be ineligible because of a protocol violation at enrolment (based on data collected prior to enrolment).
2. Participants without culture confirmation of M.tb at Day 1 (baseline) sputum samples (or screening or out to Week 4 if the baseline is contaminated or negative). These participants will be late exclusions from the study.

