### **7.1. Primary Efficacy Endpoint**

Time to culture negative status in liquid media over 8 weeks will be analysed using a Cox regression model, censoring for death and lost to follow up/withdrawal to estimate the hazard ratio. This model assumes proportional hazards. This means that the hazard rates for participant subgroups are proportional over time during participant follow-up. A program that tests the proportional hazards assumption in the Cox model (estat phtest for Stata) will be used. In the case where there is adequate evidence that the proportional hazard assumptions are violated at the 5% level (i.e.  $p<0.05$ ), then the restricted mean survival time method (RMST) will be used. Data will be described using Kaplan-Meier plots.

For the 8 week culture conversion endpoint the time will be taken from randomisation until the first occurrence of achieving culture negative status in liquid media over 8 weeks. For participants who do not achieve culture negative status, time will be taken from randomisation to 8 weeks (and censored). Participants who die or are lost to follow up/withdrawn will be considered as not achieving culture negative status unless they have achieved a culture negative status prior to death or being lost to follow up/withdrawn. The last known visit date will be taken for any participants who are missing the date of their 8-week visit. Participants negative at baseline (but eligible for the trial based on a positive result at screening) will not be included in this primary time-to-event analysis.

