### 7.4. Subgroup Analyses

As exploratory analyses to assess consistency of outcome, the following sub-group analyses (with tests for interaction) of the primary endpoint on the mITT analysis populations will be considered according to:

- HIV status
- Cavitation (images are to be reviewed in order for these data to be considered reliable)

- Age
- Sex
- Race
- Region
- Smoking status
- Alcohol intake
- Pyrazinamide resistance (pending numbers)
- Bedaquiline resistance (pending numbers)
- Time to positivity

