## 10.2. Baseline characteristics

- History of TB (type) (DS-TB, Mono-Resistant TB, MDR TB, PRE-XDR TB, XDR TB)
- Current TB type (DS-TB, DR-TB)
- Smoking status (never, current, former)
- Alcohol status (never, current, former)
- Screening mycobacteriology test result
  - Smear microscopy for acid-fast bacilli (AFB) (no AFB seen, scanty positive, 1+, 2+, 3+)
  - Rapid molecular tests for fluoroquinolones, aminoglycosides-cyclicpeptides, isoniazid, and rifampicin resistance (Hain assay MTBDRplus and MTBDRsl (sensitive, resistant, indeterminate, not done)) and MTB confirmed (Yes, No)
  - Liquid culture (MGIT) mycobacterium tuberculosis (MTB) result (negative, positive for MTB complex, positive for MTB complex with contamination, contaminated, no result) and time to positivity when positive.
- Serology
  - HIV status (positive, negative as collected in CRF)
  - CD4 count (summary statistics)
- Karnofsky performance status
- Chest X-ray (normal, abnormal)
  - Cavities (none, unilateral, bilateral)
- Ophthalmologic history
  - History of vision and/or eye disorders (yes, no)
  - Immediate family history of cataracts (yes, no)
  - History of prior eye surgery and/or trauma (yes, no)

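### Baseline time to positivity is left to an optional secondary analysis; standardising the 12-month risk difference over it would add a modest amount of power

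*SAP*

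**What the plan says.** Section 7 of the SAP fixes the main adjustment: "All efficacy analyses will be adjusted for the stratification variables (HIV status and cavitation) unless otherwise stated and considered primary". For anything beyond those two factors it says: "Additional baseline covariates listed in §7.4 will be considered for a secondary adjusted analysis for key efficacy endpoints".

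The Section 7.4 list was written for subgroup analyses. It includes "Time to positivity" with no visit and no scale. Section 10.2 places the measurement under the screening MGIT result: "contaminated, no result) and time to positivity when positive". Sections 2.5.1 and 7.2.10 point to the same list for candidate predictors of 12-month outcome.

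Section 7.2.1 analyses the 12-month difference with the Cochran-Mantel-Haenszel test. Non-inferiority is declared if the upper limit of the two-sided 95% interval is below 12%. Section 7.2.2 applies the same method at 24 months.

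On the primary endpoint, Section 7.1 says: "Time to culture negative status in liquid media over 8 weeks will be analysed using a Cox regression model".

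**The concern.** Time to positivity in liquid culture reflects bacterial load before treatment, and the SAP itself treats it as a possible predictor of 12-month outcome. The trial already holds it. A prognostic baseline variable that is left out of the analysis of a risk difference leaves the interval wider than it need be.

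This matters most for the 12-month comparison, which has 74% planned power at 150 per arm and becomes the primary endpoint if the trial expands after the interim (Section 7.3.1). There is also a gap in specification. The secondary adjusted analysis is not a commitment, and the SAP does not say which listed covariates enter, in what form, or what happens when a value is missing. A choice left open in this way can later be made with results in view.

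**Working it through.** **Inputs from the SAP**
- Section 4: 150 per arm, 16% unfavourable in control, 13% unassessable, 12% margin, two-sided 5%, stated power 74%.
- Section 4, primary endpoint: 150 per arm, HR 2, 50% of controls negative by 8 weeks, stated power above 99%.
- Section 7.3.4 and Appendix 13.4: 225 recruited and 196 analysed per arm after expansion, with 90% power at the final stage.

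**Assumed, because the SAP gives no figure:** R², the share of variance in 12-month status that time to positivity explains beyond HIV status and cavitation. Range used: 0.02 to 0.10. At a 16% event rate, odds ratios of 1.5, 2.0 and 2.5 per SD correspond to R² of 0.022, 0.062 and 0.103.

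**1. Reproduce the stated power.** Analysed per arm: 150 × (1 − 0.13) = 130.5.

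SE = √(2 × 0.16 × 0.84 / 130.5) = 0.0454

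Power = Φ(0.12/0.0454 − 1.96) = Φ(0.684) = 75.3%

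This agrees with the stated 74% to within rounding and choice of formula. With 196 analysed per arm the same formula gives 90.0%, matching the final-stage figure.

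**2. Add the covariate.** Standardisation multiplies the variance of the risk difference by about (1 − R²):

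Power = Φ(0.12/√(2 × 0.16 × 0.84 × (1 − R²)/n) − 1.96)

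| R² | 95% half-width, n = 130.5 | Power, n = 130.5 | Power, n = 196 | Equivalent extra per arm, 150/(1 − R²) − 150 |
|---|---|---|---|---|
| 0 | 8.90 points | 75.3% | 90.0% | 0 |
| 0.02 | 8.81 | 76.1% | 90.6% | 3.1 |
| 0.05 | 8.67 | 77.4% | 91.4% | 7.9 |
| 0.10 | 8.44 | 79.6% | 92.7% | 16.7 |

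**3. Primary Cox model.** Expected events at HR 2: 150 × (0.50 + 0.75) = 187.5. The Schoenfeld formula gives 99.7% power, in line with the SAP, which says that 150 per arm "will provide more than 99% power (5% two-sided significance) to detect a hazard ratio (HR) of at least 2".

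The effect of adjustment was simulated: 1,500 trials per setting, 150 per arm, censoring at 8 weeks, conditional HR 2, a normal covariate, and HIV status and cavitation not modelled.

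| Covariate HR per SD | log HR, unadjusted to adjusted | SE, unadjusted to adjusted | Mean z |
|---|---|---|---|
| 1.35 | 0.671 to 0.696 | 0.1505 to 0.1511 | 4.45 to 4.60 |
| 1.65 | 0.628 to 0.694 | 0.1509 to 0.1521 | 4.15 to 4.56 |
| 2.01 | 0.579 to 0.691 | 0.1516 to 0.1533 | 3.81 to 4.50 |

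The standard error does not fall. The estimate moves away from zero because the adjusted hazard ratio is a more conditional quantity. Power goes from between 97% and nearly 100% unadjusted to above 99% adjusted.

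Larger gains need conditions outside the main design case. At HR 1.5, power rises by about 4 to 5 points (covariate HR 1.5 per SD) or 11 to 13 points (2.0 per SD). At HR 2 with only 25% of controls converting, it rises from 90% to 92% or from 87% to 93%.

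**The case against.** Adjusting only for the stratification factors is a standard, valid and prespecified choice, and the SAP contains no mistake here. The covariate is not ignored: it is listed for the secondary adjusted analysis, the subgroup tests and the predictor analyses. All of this stands, so the point concerns efficiency only.

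The gain is assumed and small. Any overlap between cavitation and bacterial load lowers the increment. In mITT everyone who does not reach the endpoint is unfavourable (Section 6.2.1.2), and a bacterial-load measure cannot be presumed to explain loss to follow-up. Appendix 13.3 itself describes recorded outcomes in this field as diluted by missing data. This favours the lower end of the range in mITT. TB-mITT removes some of that dilution.

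The SAP also has its own route to higher power, through expansion to 225 per arm. That reduces the need for adjustment without removing the benefit, and expansion depends on the interim result and on funding.

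The change is not free of complications. Time to positivity exists only for a positive culture, and confirmation may come late ("or screening or out to Week 4 if the baseline is contaminated or negative"), so some participants will have no screening or Day 1 value. The 12-month test must also be replaced. In the Cox model, the SAP would have to say how an added covariate bears on the proportional-hazards check and the switch to restricted mean survival time.

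A reader might go further and infer that the primary hazard ratio is biased toward 1 or loses precision without this covariate. The documents do not support that. The strata-adjusted hazard ratio is a legitimate estimand, its standard error is no larger, and planned power at HR 2 is already above 99%. The larger Cox gains rest on covariate strengths that the SAP does not contain, and mostly on HR 1.5, which it does not use.

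**Conclusion.** The point holds as a low-cost improvement to the 12-month comparison, together with a gap in specification. At 150 per arm, standardising over baseline time to positivity would raise power from about 75% to between 76% and 80%, a gain of about 1 to 4 points, equivalent to about 3 to 17 more participants per arm. At 196 analysed per arm the rise is from 90.0% to 91.4% at R² = 0.05 and 92.7% at 0.10. These figures rest on an assumed R² of 0.02 to 0.10 beyond HIV status and cavitation, equal true rates of 16%, and the SAP's 13% unassessable. The standardised difference is still the marginal risk difference, so the 12% margin and decision rule carry over unchanged.

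For the primary Cox model the matter is minor. Adjustment changes the quantity estimated and does not shrink the standard error. It can add much test power only if the true effect is smaller, or conversion slower, than the main design assumes.

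**What to change.** Before unblinding, amend Sections 7 and 7.2.1 (and through it 7.2.2) as follows.

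- Make the main analysis of 12- and 24-month status a risk difference standardised over HIV status, cavitation and baseline log time to positivity.
- State the visit that supplies the baseline value. Section 10.2 names only screening, so a rule such as Day 1, else screening, must be written down.
- Handle absent values with a missing-value indicator.
- Keep the existing rule that compares the upper 95% limit with 12%.
- Report the strata-only Cochran-Mantel-Haenszel result as a sensitivity analysis.
- Replace the open statement about further covariates with a fixed list and form.

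Adding the covariate to the primary Cox model is optional. If it is done, specify its role in the proportional-hazards check and in the fallback analysis.

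The cost is SAP wording with no new data. The downsides are a few missing values, one replaced test and, if the Cox model is also changed, a hazard ratio conditional on one more covariate.
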